If unexplained elevations of BUN and/or serum creatinine ($> 20\%$) occur (per Investigator), the next cycle of treatment should be delayed until values return to baseline and the dose should be reduced to 200 mg in the next cycle of treatment. A schedule modification from 14 to 7 days (21 days to 14 days in those subjects whose dose schedule has been extended due to disease progression) can be made if the elevation in BUN and/or creatinine recurs in the subsequent cycle. Should similar unexplained renal disturbances subsequently persist or recur during the next cycle of treatment, study treatment should be discontinued.

Dose Modification for Other Treatment-Related Non-Hematologic Toxicity \geq Grade 3

Any subject who experiences a treatment-related non-hematologic toxicity Grade 3 or higher that is an escalation from baseline status (prior to first IP dose) should temporarily discontinue IP treatment until the toxicity returns to Grade 2 or lower. Dose modifications for Grade 3 or higher non-hematologic toxicity are summarized in Section [8.2.5](#).

Dose Modification for Weight Change

No dose adjustment should be made for weight loss or gain alone; however, the reason for weight loss (eg, significant nausea, vomiting, anorexia, etc.) or weight gain (eg, peripheral edema) should be investigated and may require a dose modification as specified in Section 8.2.5.

Table 2: Guidelines for Dose Modifications

NCI-CTCAE Toxicity Grade	Action

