
Renal Dysfunction
	
 • For unexplained elevations of BUN and/or serum creatinine (> 20%), hold IP, if this is apparent during the IP administration phase and/or delay the start of the next cycle of treatment until values return to baseline (± 20%). Reduce IP dose in the next cycle of treatment to 200 mg. • Discontinue IP if similar unexplained renal and/or electrolyte disturbances subsequently persist or recur during the next cycle of treatment. • (Treatment schedule modification requires prior discussion with Medical Monitor).

Other ≥ Grade 3 non-hematological treatment-related AEs
	
 • Interrupt IP dosing and provide medical intervention as appropriate • Resume IP at same dose when toxicity resolves to ≤ Grade 2 • If event reoccurs upon re-challenge or at same intensity during next treatment cycle, reduce IP dose to 200 mg • If event reoccurs at same intensity once dose is reduced to 200 mg, follow the steps above and modify treatment schedule from 14 to 7 days (21 days to 14 days for those subjects whose dose schedule has been extended due to disease progression) of IP administration. (Treatment schedule modification requires prior discussion with Medical Monitor).

AE=Adverse Event; ANC=Absolute Neutrophil Count; CTCAE=Common Terminology Criteria for Adverse Events; NCI=National Cancer Institute; IP=Investigational Product.

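### Protocol Section 8.2.5 and its Table 2 order the steps differently when unexplained renal toxicity recurs at 200 mg, so the stopping point depends on which page is followed

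*Protocol*

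**What the plan says.** Both versions sit in Protocol Section 8.2.5 and are triggered by an unexplained elevation of BUN and/or creatinine above 20%.

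- **Renal paragraph.** After the first event, "the next cycle of treatment should be delayed until values return to baseline and the dose should be reduced to 200 mg" for that cycle. A schedule modification (14 to 7 days, or 21 to 14 days for subjects on the extended schedule) "can be made if the elevation in BUN and/or creatinine recurs in the subsequent cycle". The last sentence reads: "Should similar unexplained renal disturbances subsequently persist or recur during the next cycle of treatment, study treatment should be discontinued".
- **Table 2, renal row.** Hold IP if the rise appears on dosing days and/or delay the next cycle. As far as the percent sign, the restart wording is "delay the start of the next cycle of treatment until values return to baseline (± 20". Then "Reduce IP dose in the next cycle of treatment to 200 mg". The next bullet is "Discontinue IP if similar unexplained renal and/or electrolyte disturbances subsequently persist or recur during the next cycle of treatment". A final bracketed bullet says that a schedule change must first be discussed with the Medical Monitor, but gives no trigger for making one.

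The opening rules of 8.2.5 allow one reduction to 200 mg and then one schedule modification if toxicity does not respond to the reduction, after discussion with the Medical Monitor. Appendix K sends Extension Phase dose modifications back to 8.2.5.

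**The concern.** This is a safety rule on stopping treatment, stated twice in one section, and nothing in the section says whether the paragraph or the table prevails. If they disagree on what follows a recurrence, about 180 sites (Protocol Section 7.1) have two written instructions for the same finding. An investigator who continues on a modified schedule follows the paragraph but departs from the table.

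The stopping point also feeds a secondary endpoint. Time to discontinuation from treatment is analysed by reason, with adverse events as one of the reasons (Protocol Section 10.6.2.2; SAP Section 11.3.2). Because the Extension Phase uses the same section, the ambiguity carries forward into it.

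**Working it through.** No sample size, power or event figure bears on this point. The check sets the two sequences side by side, with the first event in cycle k.

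| Step | Renal paragraph | Table 2 renal row |
|---|---|---|
| First event, cycle k | Delay; 200 mg in cycle k+1 | Hold and/or delay; 200 mg in cycle k+1 |
| Recurrence in cycle k+1 at 200 mg | Schedule modification permitted | Discontinue |
| Persistence or recurrence in cycle k+2, if the schedule was modified | Discontinue | Not reached |

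**Stopping point.** The discontinuation sentences are almost the same, and both refer to the next cycle. In the paragraph that sentence follows the schedule step, so the next cycle is k+2. In the table it follows the dose reduction, so the next cycle is k+1. The sequences differ by one step.

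**Do other parts of 8.2.5 settle it?**

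- The general rule permits one schedule modification but does not say whether it comes before the stop in the renal row.
- The Medical Monitor bullet sets a condition on changing the schedule without placing the change in the sequence.
- The rows for febrile neutropenia, diarrhea and other Grade 3 or higher non-hematological events state the 14-to-7 (or 21-to-14) step outright. The nausea/vomiting row does not, but it has no instruction to stop treatment, so nothing there conflicts.
- The renal row alone leaves the step unstated and ends in stopping. A reader cannot tell omission from intent.

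**Restart condition, as a multiple of the subject's own baseline.** The trigger is above 1.20 in both places. Read literally, the paragraph requires a return to 1.00, while Table 2 accepts 0.80 to 1.20. Under that literal reading a subject at 1.10 waits under the paragraph and may start under the table. If return to baseline means no longer exceeding the 20% trigger, the upper limit is 1.20 in both and the difference disappears.

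**Link to Section 8.2.7.** The next cycle also requires the renal entry criterion (creatinine no more than 2.5 times ULN, Section 7.2). A delay of more than 56 days leads to discontinuation unless the subject is judged to be benefiting. A stricter restart reading would therefore use up more of that allowance.

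**The case against.** The best defence is that the opening rules of 8.2.5 govern the whole section, Table 2 included. On that view the Medical Monitor bullet would be pointless unless a schedule change were available for renal events, so the table relies on the general rule. The paragraph's step is also optional, so stopping at the first recurrence breaches neither page. The table is headed as guidelines. Schedule changes go through the Medical Monitor, and Sections 6.13 and 8.2.1 ask for contact before a subject is discontinued.

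Much of this stands, and it limits the point. It does not say whether the table's stop falls before or after the schedule step. The contact safeguard is also incomplete: Section 8.2.7 asks for contact before discontinuation for reasons other than those listed in 8.2.5, which can be read as exempting these cases.

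A reader might infer more than the documents support:

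- **That every recurrence changes exposure by at least one 28-day cycle.** It does not follow. The paragraph's step is optional, and a subject who takes it may still stop early.
- **That the restart rules plainly conflict.** They do so only if the paragraph demands exact equality with baseline.
- **That Table 2 adds an electrolyte trigger and a new power to hold drug.** Electrolytes appear only in its stopping bullet and are named in the paragraph's own heading. Interruption is already allowed by the opening rules of 8.2.5.
- **That RFS is distorted because scheduled marrows end at discontinuation.** Relapse follow-up with supporting reports continues afterwards (Section 6.14), SAP Section 11.3.1 plans an investigator-assessed sensitivity analysis, and no effect is shown.

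**Conclusion.** The inconsistency is real and lies in the current text. For a recurrence in the first 200 mg cycle, the paragraph permits a further step before stopping, while the table directs stopping with no such step stated. The restart wording is a secondary difference and may be only a matter of explicitness.

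The size cannot be given as a number. The protocol states no expected count of renal recurrences, and exposure can differ but need not. Both arms follow the same wording under blinding, and time to discontinuation lies outside the alpha-controlled sequence of OS then RFS. No effect on OS, RFS, power or alpha is shown.

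The conclusion rests on reading the steps in the order in which they are printed. It takes no position on which clinical rule is right.

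**What to change.** Reconcile the renal paragraph and the Table 2 renal row, together with the opening rules of 8.2.5 and the re-treatment criteria in 8.2.7, so that there is one restart condition, one order of steps and one stopping point. Attach the Medical Monitor note to a stated step or remove it. State that the result applies in the Extension Phase through Appendix K. The clinical team decides the content.

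The cost is a protocol wording change or a clarification letter to sites. No analysis, sample size or endpoint definition needs to change.

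This should be done because it is a safety stopping rule and cheap to correct, not because a statistical result depends on it.

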8.2.6. Dose and Schedule Adjustment in Subjects with AML Relapse/Progression

In subjects on study who have subsequent evidence of AML relapse with blasts > 5% either in the peripheral blood count or bone marrow, and provided the blasts are no greater than 15% in the blood or bone marrow, escalation of the dosing regimen (dose and/or schedule) can be implemented as follows (provided it is in the best interest to do so as judged by the Investigator):

- Subject currently on blinded treatment of oral azacitidine 300 mg or placebo QD for 14 days - escalate schedule to oral azacitidine 300 mg or placebo QD for 21 days
- Subject currently on blinded treatment of oral azacitidine 200 mg or placebo QD for 14 days - escalate dose schedule, as a first step, to oral azacitidine 200 mg or placebo QD for 21 days and then escalate dose to oral azacitidine 300 mg or placebo QD for 21 days
- Subject currently on blinded treatment for oral azacitidine 200 mg or placebo QD for 7 days - escalate dose schedule, as a first step, to oral azacitidine 200 mg or placebo QD for 14 days and then escalate dose to oral azacitidine 300 mg or placebo QD for 14 days

In cases where relapse is noted within a week of starting the next cycle, and there is a desire to escalate the dose schedule during the cycle, contact the Medical Monitor to discuss this, in order to obtain the additional required IP.

8.2.7. Re-treatment Criteria

Prior to the start of each cycle, subjects will have laboratory assessments performed to evaluate organ function. In order to proceed to the next cycle, subjects must continue to meet entry criteria regarding renal and hepatic function (see Section 7.2). Thus, subjects will have laboratory assessments performed to evaluate organ function prior to starting each cycle (including Cycle 1). Because of the time it takes to obtain results from the central laboratory, samples should be collected early enough prior to starting the next cycle in order to allow sufficient time for review. In the event that immediate laboratory assessment is needed, local laboratory measurement is acceptable for starting the next cycle pending the outcome of the central laboratory assessment (ie, in addition to collecting the local laboratory sample, a second sample should be collected and sent to the central laboratory).

The start of the next cycle will be delayed if the subject does not meet entry criteria regarding renal and hepatic function. If there is a delay of more than 42 days (6 weeks) in the start of the next cycle, the Medical Monitor must be consulted. Study treatment should be discontinued if there is a delay of more than 56 days (8 weeks) in the start of the next cycle, unless, in the opinion of the investigator and the Medical Monitor, the subject is experiencing clinical benefit. Justification of the subject continuing in the study must be recorded in the source documents.

Prior to discontinuing a subject for reasons other than those listed in Section 8.2.5, the investigator should contact the Medical Monitor and forward appropriate supporting documents for review and discussion.

8.3. Method of Treatment Assignment

Subjects approved for enrollment will be randomized to receive oral azacitidine or placebo in a 1:1 ratio. Randomization will be accomplished by an IVRS to ensure timely registration and randomization. A stratified blocked randomization schedule will be implemented.

Investigator or designated site staff will be assigned password protected, coded identification numbers that give them authorization to call into the IVRS to enroll subjects. At screening, the investigator or designated staff will call into the IVRS and provide the requested identifying information for the subject. The IVRS will then confirm the assignment of a 2-part unique subject number. The first part is the center number and the second part is one of a series of

numbers allocated to subjects at that center. Once assigned to a subject, the subject number will not be reused. If the subject is not randomized, the IVRS must be notified.

Randomization will be performed using the following procedure to ensure that treatment assignment is unbiased and concealed from subjects and investigators. A subject randomization list will be produced by the IVRS provider using a validated system that automates the random assignment of subject numbers to randomization numbers. These randomization numbers are linked to the different treatment groups. The randomization scheme for subjects will be reviewed and approved by the Biostatistics Group of the sponsor, Celgene Corporation. Written consent must be obtained, all the screening evaluations must be completed, and eligibility criteria must be verified by the sponsor *prior* to randomizing a subject. Then the investigator or designated staff will call the IVRS and confirm that the subject fulfills all the inclusion and exclusion criteria. The IVRS will assign a randomization number to the subject, which will be used to link the subject to a treatment group.

A stratified randomization schedule will be implemented. Subjects will be stratified by: age at time of induction therapy (55-64 years and ≥ 65 years), prior history of MDS or CMML (Yes / No), cytogenetic risk category at time of induction therapy (Intermediate risk / Poor risk) and received consolidation therapy following induction (Yes / No). The random treatment assignment will be concealed so that investigators and subjects will not know in advance the next treatment assignment.

After randomization, no crossover between the treatment arms will be permitted. Subjects may continue to receive randomized study treatment for as long as it is appropriate, provided that all protocol-specified re-treatment criteria are met.

8.4. Packaging and Labeling

The label(s) for IP will include sponsor name, address and telephone number, the protocol number, IP name, dosage form and strength (where applicable), amount of IP per container, lot number, expiry date (where applicable), medication identification/kit number, dosing instructions, storage conditions, and required caution statements and/or regulatory statements as applicable. Additional information may be included on the label as applicable per local regulations.

8.5. Clinical Supplies

The investigator(s) or designee(s) is responsible for taking an inventory of each shipment of IP received, and comparing it with the accompanying study drug shipping order form. The investigator(s) or designee(s) will verify the accuracy of the information on the form and call the IVRS to register the study medication received at the site.

At the study site, all IPs will be stored according to the storage conditions described on the IP packaging label in a locked, safe area to prevent unauthorized access. The IP must be stored as directed on package label at controlled temperature and a temperature log must be maintained in the source documents.

8.6. Investigational Product Accountability and Disposal

Investigational Product accountability will be assessed by the investigator or designee. Applicable information such as lot number, tablet count and expiration date should be collected, as well as information provided by the subject or the caregiver (eg, subject dosing diary).

Investigational Product accountability should be assessed before drug dispensing for each subsequent treatment cycle in the treatment phase, starting on Day 1 of Cycle 2, and at the Treatment Discontinuation visit.

The investigator(s) or designee(s) is responsible for accounting for all IP that is issued to and returned by the subject during the course of the study according to applicable regulatory requirements. Any unused IP must be returned by a study subject and retained by the investigative site for accountability to be conducted by a Celgene representative (or designee). If any IP is lost or damaged, its disposition should be documented. At the periodic monitoring visits, a Celgene representative (or designee) will conduct IP accountability and address any discrepancies. Upon satisfactory reconciliation of all IP, returned IP may be destroyed. At the conclusion of the study, all remaining study drug will be counted, reconciled with dispensing records, documented, and destroyed at the clinic site or allocated drug destruction location after completion of drug accountability by a Celgene representative (or designee). The Celgene representative (or designee) will ensure that a final report of drug accountability to the unit dose level (ie, tablet) is prepared and placed in both the investigator study file and the central clinical study file.

Celgene Corporation will instruct the investigator(s) on the return, disposal and destruction of IP. A copy of the site's Standard Operating Procedure (SOP) for drug destruction may be collected by the sponsor (or designee). Any revisions to a site's destruction process must be provided and approved by the sponsor (or designee) prior to implementation on this protocol. Any site without a sponsor (or designee) approved destruction SOP and process will be required to return IP to Celgene.

8.7. Investigational Product Compliance

Investigational Product will be administered by the study site personnel in the clinic on PK sampling days. Subjects will self-administer all other IP doses in the treatment phase. Documentation of dosing during treatment will be recorded in a study specific diary card. Investigational product administration diary cards will be provided by the sponsor to study site personnel, who will in turn distribute them to study subjects. Study site personnel will enter the scheduled daily doses, the number of tablets to be taken each day and any other applicable information. Study site personnel will review the dosing information with the subject (or legally authorized representative) on scheduled clinic visit days. Subjects (or legally authorized representative) will be asked to record IP dosing information and anti-emetic medication taken at home in the diary card and to bring the diary card and unused tablets in the blister card (or the blister card packaging even if it is empty) with them to scheduled clinic visits (ie, prior to the start of the next treatment cycle). A diary card and tablet compliance check will be performed by study personnel. Diary cards must be saved and kept with the source documentation. Study site personnel will perform an IP administration compliance check and record this information in the subject's source documentation and on the appropriate CRF.

Administration of all IP will be recorded including dispensing, dosing and any changes in dosage administration such as interruption or reduction in dosing due to an AE.

8.8. Blinding

This is a double-blind study. Subjects, investigators, site staff and Celgene Corporation clinical and medical personnel will be unaware of treatment assignments until study closure and database lock.

8.9. Emergency Unblinding

In order to maintain the integrity of the study design, the blind must not be broken during the course of the study unless, in the opinion of the investigator, it is absolutely required to safely treat the subject. There should be only rare instances when breaking the blind would be required, such as the development of pregnancy, for example. In most instances of treatment-related toxicity, interrupting treatment and/or dose reduction of IP is all that would be required. For more information on the unblinding process, please refer to Section [13.2](#).

[REDACTED]

[REDACTED]

[REDACTED]

[REDACTED]

- [REDACTED]
- [REDACTED]
- [REDACTED]
- [REDACTED]
- [REDACTED]
- [REDACTED]
- [REDACTED]
- [REDACTED]
- [REDACTED]
- [REDACTED]

[REDACTED]

[REDACTED]

10. STATISTICAL ANALYSES

10.1. Overview

This Phase 3, multicenter, randomized, double-blind, placebo-controlled, parallel-group study is designed to compare the efficacy and safety of oral azacitidine plus best supportive care versus placebo plus best supportive care in subjects with AML who have achieved CR/CRi following induction, with or without consolidation, chemotherapy.

All data will be summarized by treatment group. In addition, where appropriate, a total column will be included to summarize subjects across treatment groups. Summaries of continuous variables will present the number of subjects included in the analysis (N), the mean and standard deviation (SD) of the mean, the median, the minimum, and the maximum statistics. Counts and percentages will be presented in summaries of categorical variables. The denominator for each percentage will be the number of subjects in the population treatment group unless otherwise specified. In general, missing data will not be imputed unless otherwise specified.

10.2. Study Population Definitions

10.2.1. Intent-to-Treat Population

The intent-to-treat (ITT) population includes all subjects who are randomized to treatment, regardless of whether they received treatment or not. All efficacy analyses will be conducted for the ITT population. Subjects will be analyzed based on randomized treatment group.

10.2.2. Modified Intent-to-Treat Population

The modified intent-to-treat (mITT) population includes all subjects who have met all inclusion/exclusion criteria and experienced no major protocol deviations during the study, and received a minimum of one cycle of treatment. Subjects who are randomized without confirmed CR/CRi per central review will be excluded from the mITT population. This definition will be further clarified and detailed in the final statistical analysis plan prior to database lock.

Key efficacy analysis will be performed for the mITT population as supportive and/or exploratory analysis only. Subjects will be analyzed based on randomized treatment group.

